- **C.2.** Specific Aim 2: Is premenopausal HypoE associated with relatively endothelial dysfunction? To establish whether subclinical atherosclerosis is greater in premenopausal HypoE compared to regularly cycling women and recently postmenopausal women using peripheral arterial tonometry (PAT).
- **C.2.1. Data Collection:** Measure of Vascular Function: PAT is a proven, non-invasive measure of vascular function is method of detecting endothelial function by Endo PAT 2000 (Itamar® Medical Ltd), which we and others including the Framingham Study have successfully used. ⁴² The device consists of a finger probe to assess digital volume changes accompanying pulse-waves. A pressure of 40-70mmHg is applied by the probe to the index fingers of both hands to eliminate venous stasis and arterial pulse amplitude is recorded. Device calculates a reactive hyperemia peripheral arterial tonometry (RH-PAT) index, which reflects peripheral vascular function.
- C.3. Specific Aim 3: To determine that estrogen improves CVD inflammatory biomarkers and markers of subclinical CVD in premenopausal HypoE women. In a randomized, double-blind placebo-controlled trial in premenopausal HypoE women we will test 12 weeks of transdermal estradiol on inflammatory biomarkers and subclinical CVD versus placebo at baseline and 12 weeks followed by 2 weeks of estradiol plus progesterone for endometrial safety.
- 30 HypoE women will be randomized to transdermal estrogen for 12 wks followed by transdermal estrogen plus oral progesterone for 2 weeks. We will compare markers of endothelial function and inflammatory response at baseline and 12wks in women randomized to hormone therapy vs placebo.

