- **C.3.1. Rationale.** Estrogen treatment has been shown to improve vascular function in women with premature menopause and it is well established that estrogen has immune-modulating effects resulting in lower pro-inflammatory cytokines in postmenopausal women. We will use our PAT index as a vascular function measure of pre-clinical CVD. We will use a dose of transdermal estradiol 0.1 mg/day weekly patch for 12 wks, which will result in a mean serum estradiol level of 70 pg/ml.⁴³ We are working with the manufacturer to obtain placebo patches as has been done in previous double-blinded studies.⁴⁴ Patches will be applied by the subject to the lower abdomen twice weekly, alternating sides. The dose and 12 week duration of unopposed transdermal estradiol was selected based on prior study to maintain serum around 75 pgram and to minimize the risk of endometrial hyperplasia.⁴⁵ The use of unopposed estradiol at higher doses and longer duration can result in endometrial hyperplasia in postmenopausal women after one to three years. Our 12 week treatment of estrogen will be followed by 2 weeks of estrogen and progesterone to allow sloughing of the endometrium and reversal of the estrogen effect on the endometrium.⁴⁶ This dose is equivalent to an average serum estradiol level in an ovulating woman which ranges from 50 up to 400 pg/ml.⁴⁷ We selected a 0.1mg/day dose of transdermal estrogen

to provide a more physiologic estradiol level compared to oral estradiol which is rapidly convert to estrone. After 12 wks of transdermal estradiol, we will continue estradiol and add oral micronized progesterone 200mg for 14 days to mimic the luteal phase and will allow us to evaluate the additional impact of estrogen plus progesterone. Progesterone 200mg is a peanut based product and for patients with a peanut allergy we will replace this with a synthetic progestin at an equivalent dose, medroxyprogesterone 10mg. This is an FDA-approved medication and has the same indication.

C.3.2. Hypothesis. We hypothesize that estradiol treatment will improve vascular endothelial function, and markers of inflammation in premenopausal HypoE women.

C.3.3. Experimental Protocol and Data Collection: Baseline serum hormones, vascular measures, and immune markers will be collected from aims 1 and 2 in the 30 HypoE women. Subjects will then be randomized to 0.1mg/day transdermal estradiol patch or placebo for 12 weeks followed by 2 weeks of estradiol patch

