with progesterone or placebo pills with placebo patch for 12 weeks +/- 1 week and 2 weeks +/- 3 days after completing estrogen and progesterone (**Figure**). One week after completing the patch and pill, study staff will contact participant and ask if they had their menstrual period. If needed, 1 patch and 3 more pills will be dispensed during the week 12 visit to account for patient schedules if they cannot come in exactly at day 14, as the exit visit on study drug is needed as suggested by the pharmacist.

- **C.3.4. Data Collection:** Serum hormone evaluation: After 7 days of transdermal 17-beta estradiol and 12 weeks we will measure serum E2 levels and hormone panel to assess blood levels and compliance. Vascular measures will be tested at baseline and 12 week. Detailed method collection described under Aim 1A.
- C.3.5. Data Analysis. Statistical method: Associations between change in serum estrogen, change in PAT, change in inflammatory marker levels will be examined. Pearson correlations will be examined between continuous variables. If the distributions are non-normal Spearman correlations will be used. A linear mixed model will be used on the change in PAT at week 12 to examine the association while adjusting for within subject correlation. In addition to choosing an appropriate correlation structure, other model building and diagnostics will be carried out as described in Aim1A. A Tukey-Kramer or Bonferroni adjustment for multiple pair-wise comparisons will be used as appropriate.

Power considerations: Pilot data indicated a baseline SD of 0.35 for PAT in the HypoE group and 0.44 in the control group. Assuming the larger SD at baseline and 4 weeks, a conservative estimate of the SD for the change in PAT assuming no correlation, would be the square root of the sum of the variance estimates at both time points, which is about 0.622. A sample of 15 women in the placebo group and 15 in the treatment group for change in PAT using a two sample t test with 80% power at a significance level of 0.0167 would allow detection of a difference of at least 0.78 units when the sample SD is 0.622. The significance of 0.0167 was chosen by dividing 0.05 by three for the number of comparisons between groups. Increasing correlation above zero between pre and post PAT values will give more precision and allow detection of smaller differences (e.g. a correlation of 0.8 allows detection of a difference of at least 0.35 units).

References:

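### Section C.3.5 divides alpha by three for between-group comparisons, but Aim 3 has two arms and a single between-group comparison of change in PAT

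*Combined protocol and SAP*

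**What the plan says.** **Level and reason (C.3.5, power considerations).** "The significance of 0.0167 was chosen by dividing 0.05 by three for the number of comparisons between groups". The calculation is for "A sample of 15 women in the placebo group and 15 in the treatment group for change in PAT using a two sample t test". It assumes power of 80% and an SD of change of 0.622, and gives a detectable difference of 0.78 units with no pre-post correlation. The paragraph adds: "Increasing correlation above zero between pre and post PAT values will give more precision and allow detection of smaller differences", with 0.35 units at a correlation of 0.8 as its example.

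**Design.** C.3.3: "Subjects will then be randomized to 0.1mg/day transdermal estradiol patch or placebo for 12 weeks". C.3: "We will compare markers of endothelial function and inflammatory response at baseline and 12wks in women randomized to hormone therapy vs placebo". C.3.4 says that vascular measures "will be tested at baseline and 12 week".

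**Analysis (C.3.5, data analysis).** "A linear mixed model will be used on the change in PAT at week 12", and "A Tukey-Kramer or Bonferroni adjustment for multiple pair-wise comparisons will be used as appropriate". This text gives no significance level.

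**The concern.** A Bonferroni divisor should equal the number of tests that share the error rate. The reason given here is a count of comparisons between groups, and the calculation it supports names two groups, which can be compared in only one way. No list of three comparisons appears anywhere in the document.

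Two things are at stake. First, the published detectable differences are larger than a single contrast at two-sided 0.05 would need. Second, the reader cannot tell which level will decide the PAT result. The value 0.0167 appears only under power considerations, and the analysis text leaves pairwise adjustment to judgement, although a single two-arm contrast has no set of pairwise comparisons to adjust. A PAT p-value between 0.0167 and 0.05 could be read either way after the fact.

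**Working it through.** **1. Can the design supply three between-group comparisons of change in PAT?**

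- *Arms.* Two, estradiol and placebo (C.3, C.3.3), which gives one comparison.
- *Time points.* C.3.4 sets vascular measures at baseline and week 12, which gives one change score. The power paragraph calls the second time point 4 weeks, but it too has only one follow-up. C.3.1 mentions evaluating the added effect of progesterone, but no PAT measurement is scheduled for that phase.
- *Cohorts.* Aims 1 and 2 have three groups (HypoE, regularly cycling, recently postmenopausal), hence three possible pairs. The cycling and postmenopausal women are not randomised and no week-12 PAT is described for them, so they cannot enter a comparison of change.
- *Outcomes.* Inflammatory markers are also compared between arms, but they are outcomes, not groups, and the calculation concerns PAT alone.

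The count is one. The document does not say where the three came from.

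**2. Reproducing the stated figures.**

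Inputs from C.3.5: 15 per arm, SD 0.44 at each time point (the control-group pilot value, the larger of 0.44 and 0.35), 80% power, alpha 0.05/3 = 0.0167. Sidedness is not stated.

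SD of change = 0.44 × √(2(1 − r)), which is 0.622 at r = 0, 0.440 at r = 0.5 and 0.278 at r = 0.8.

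Two-sample t test, df = 28. Power is the probability that a noncentral t with noncentrality λ = δ / (SD × √(2/15)) exceeds the critical value. Solving for 80% power:

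- two-sided 0.0167: critical t = 2.546, λ = 3.412, so δ = 3.412 × √(2/15) × SD = 1.246 × SD
- two-sided 0.05: critical t = 2.048, λ = 2.902, so δ = 1.060 × SD

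At 0.0167 this gives 1.246 × 0.622 = 0.775 and 1.246 × 0.278 = 0.347, in line with the stated 0.78 and 0.35. A one-sided t test would give 0.703 at r = 0, so the plan's figures are two-sided. The arithmetic is sound; only the reason for the divisor fails.

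**3. Detectable difference at 80% power, one contrast at 0.05 instead.**

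| SD per time point | r | at 0.0167 | at 0.05 |
|---|---|---|---|
| 0.44 | 0 | 0.78 | 0.66 |
| 0.44 | 0.5 | 0.55 | 0.47 |
| 0.44 | 0.8 | 0.35 | 0.29 |
| 0.35 (HypoE pilot) | 0 | 0.62 | 0.52 |
| 0.35 | 0.5 | 0.44 | 0.37 |
| 0.35 | 0.8 | 0.28 | 0.23 |

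The ratio is 1.060 / 1.246 = 0.85 throughout.

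**4. Power if the final test does use 0.0167.** The document states no expected effect, so a range is shown. Each cell is power at 0.05, then at 0.0167.

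| True difference | SD 0.44, r = 0 | SD 0.44, r = 0.5 | SD 0.44, r = 0.8 | SD 0.35, r = 0 |
|---|---|---|---|---|
| 0.78 | 91%, 81% | 99.7%, 98.6% | about 100%, both | 99%, 96% |
| 0.66 | 80%, 64% | 98%, 93% | about 100%, both | 94%, 86% |
| 0.35 | 32%, 18% | 56%, 37% | 91%, 81% | 46%, 29% |

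The gap is widest at a true difference of about 0.84 SD of change, where power is 61% at 0.05 and 42% at 0.0167, a loss of 19 points. With SD 0.44 that is 0.52 units at r = 0, 0.37 at r = 0.5 and 0.23 at r = 0.8.

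**The case against.** **The cost is conditional.** A reader might infer that the trial has thrown away power. The document does not support that as a fact. The value 0.0167 is a planning figure, and nothing in the analysis text commits the final test to it. For one contrast, adjusting only where appropriate can mean not adjusting at all. If the test is run at 0.05, no power is lost. This stands in full.

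**The striking losses need pessimistic inputs.** The fall from 80% to 64% at 0.66 units takes both zero correlation and the control-group SD. With the HypoE pilot SD of 0.35 and r = 0 it is 94% to 86%. This also stands, although the 19-point maximum remains and moves to smaller differences.

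**Enrolment does not turn on it.** Section C.1.1 fixes 30 HypoE women, and the power paragraph solves for a difference with that number given. Correct: no sample-size error follows.

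**Aim 3 has more than one test.** C.3.2 hypothesises effects on endothelial function and on inflammatory markers, so a divided alpha may have a sound basis under the wrong label. That is possible, and the fix allows for it. It does not rescue the reason as written, which counts groups.

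**The three may be carried over from the three cohorts of Aims 1 and 2.** This is plausible, but the document does not say so, and it cannot be asserted.

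**Conclusion.** The stated reason for 0.0167 is wrong as written: Aim 3 offers one between-group comparison of change in PAT, not three. The error is conservative. Type I error is not inflated, and the plan's figures follow correctly from the level it chose.

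For a single contrast at two-sided 0.05, the detectable differences are overstated by about 0.12 units at r = 0 (0.775 − 0.659) and 0.05 at r = 0.8 (0.347 − 0.295). This rests on 15 evaluable women per arm, SD 0.44 at both time points and 80% power.

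The main practical defect is that the alpha for the final PAT test is unclear. The effect on power ranges from none, if 0.05 is used, to at most 19 points, if 0.0167 is used. It should be corrected, but it does not threaten the validity of the comparison.

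**What to change.** Settle one of two options before unblinding.

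1. *If the estradiol-placebo difference in change in PAT is the single confirmatory Aim 3 test:* remove the division by three and the pairwise adjustment, test at two-sided 0.05, restate the detectable differences as about 0.66 (r = 0) and 0.29 (r = 0.8), and label the inflammatory markers as secondary.
2. *If three Aim 3 tests were meant to share alpha:* name them, keep 0.0167 and the present figures, and replace the count of group comparisons with that reason.

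In either case, state the chosen alpha and that it is two-sided in the C.3.5 analysis text.

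The cost is wording and, under option 1, two restated figures; no patients or procedures change. The downside of option 1 is that it relaxes the only threshold written in the document and gives no multiplicity control for the inflammatory markers. Option 2 keeps the stricter level and accepts the power loss shown above.
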